The Summary of Product Characteristics of sunitinib is part of this observational plan.

Information on Inlyta® (axitinib)

The oral multikinase inhibitor Inlyta® (active substance axitinib) is a "small molecule". Axitinib is a potent and highly selective tyrosine kinase inhibitor of the vascular endothelial growth factor receptors VEGFR-1, VEGFR-2, and VEGFR-3, involved in pathological angiogenesis, tumor growth, and metastases. Axitinib has been shown to be a potent inhibitor of VEGF-mediated endothelial cell proliferation and cell survival. Inlyta® is used according to the Summary of Product Characteristics. The named contraindications, warnings and precautions for use, side effects, interactions and instructions on the dose, type and duration of the application should be observed.

[figure not shown]

The Summary of Product Characteristics of axitinib is part of this observational plan.

Patient Interview Advanced RCC

For the patient interview, the validated FKSI-15 questionnaire and the validated EQ-5D questionnaire/VAS will be used to document the effect of the substances temsirolimus and/or sunitinib and/or axitinib by the patient.

The Functional Assessment of Cancer Therapy-Kidney Symptom Index-15 (FKSI-15) includes 15 questions subdivided into 4 groups. Signs and symptoms, respiratory symptoms, quality of life, emotional symptoms. EuroQol-5D (EQ-5D) includes EQ-5D Index and EQ-Visual Analog Scale (VAS). The EQ-5D in turn is divided into 5 groups: Mobility, independence, usual activities, pain/discomfort, and anxiety/depression.

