Separate evaluations for third line use of axitinib following prior therapy with sunitinib in the first line followed by e.g. nivolumab, cabozantinib, or lenvatinib/everolimus in the second line are urgently needed. The efficacy of axitinib can continue to be documented after directly preceding therapy with sunitinib. These investigations allow a comparison of the efficacy and tolerability of axitinib in different lines.

Therefore, the following information is of particular interest during the course of the investigation:

- Efficacy (maximum response, survival time, progression-free time)
- Treatment tolerability (assessment by physician)
- Safety profile (overall incidence of adverse events and rate of side effects) of patients with advanced RCC, r/rMCL and GIST receiving treatment with temsirolimus, sunitinib, or axitinib
- Profile, comorbidities and characteristics of patients receiving treatment with temsirolimus, sunitinib, or axitinib
- The sequence of systemic therapies for advanced RCC, MCL, and GIST
- Patient interview on quality of life in advanced RCC patients

Temporal sequence

The following time points were defined as the minimum period for the implementation of the registry:

- Patient Recruitment Phase: January 2008 December 2020
- Recruitment rate: 100 patients/year per product
- Average observation period per patient: 6 months for temsirolimus, 12 months for sunitinib, 6 months for axitinib
- Field Phase: December 2021
- Total duration: 14 years + 1 year evaluation and report (2022)

Since the goal is to keep patients in the registry for life, the registry can be continued indefinitely.

The end of data collection is scheduled for December 2021.

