11. METHODOLOGY

The registry is designed to document the disease progression in patients with advanced renal cell carcinoma, relapsed/refractory mantle cell lymphoma, and gastrointestinal stromal tumor intended by the treating physician for systemic therapy.

During the course of the registry, the following (minimum) number of survey times and endpoints are planned:

At observation start: Enrollment Visit

During the course of the observation: Follow-up documentation (as per local guidelines, generally every

8 - 12 weeks)

End of observation: Completion/Discontinuation Form

1-year follow-up for subjects who discontinue therapy: Survival form (every 6 months thereafter)

[figure not shown]
The temporal sequence and number of follow-up documentation items depends on medical practice to perform confirmatory imaging procedures and patient survival.

The completion of the continuous observation documentation (follow-up visits) takes place with the completion or discontinuation of the case report form below:

- Patient death.
- Patient lost to follow up due to patient request/withdrawal of patient informed consent,
- Change in therapy or discontinuation due to intolerance to temsirolimus, sunitinib, and axitinib or progression.

For the indication **metastatic renal cell carcinoma**, prospective documentation of sequential therapy is an option. According to the approvals of temsirolimus, sunitinib and axitinib, e.g. the following therapy sequences are possible:

• Sunitinib (as first-line therapy) followed by axitinib

- Temsirolimus (as first-line therapy) followed by sunitinib
- Axitinib (as second-line therapy, 1st Pfizer therapy sequence) followed by sunitinib
- Sunitinib (as first-line therapy) followed by a second-line approved active substance (interim documentation) followed by axitinib (in the third line or a later line)

Herein two consecutive Pfizer lines of therapy or two Pfizer lines of therapy with one or more intermediate therapies can be documented. The following documentation sheets are available for this purpose:

White documentation section: 1. Pfizer Therapy sequenze, e.g. Sunitinib

- Enrollment Visit
- Follow-up documentation every 8-12 weeks
- Final Assessment/Discontinuation of documentation

Pink Documentation section. Interim documentation for non-Pfizer products, e.g. nivolumab

• Every 8-12 weeks

Green documentation section. 1. Pfizer Therapy Sequence

- Initial visit to change treatment
- Follow-up documentation every 8-12 weeks

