- Final Assessment/Discontinuation of documentation

Survival Sheets

After two documented Pfizer therapy sequences for advanced RCC, or if the treatment of advanced RCC, mantle cell lymphoma or gastrointestinal stromal tumor is terminated, the documentation changes to the "survival sheets".

The query will be initiated for the first time 12 months after the final visit, then every 6 months thereafter. For this purpose, a separate case report form will be provided to you by Winicker Norimed.

[figure not shown]
The patient interview in the indication area will be conducted during therapy with temsirolimus, sunitinib and axitinib at each visit.

For the indications mantle cell lymphoma and gastrointestinal stromal tumors, only

the documentation for temsirolimus and sunitinib should be used:

- Enrollment Visit
- Follow-up documentation (as per local guidelines, generally every 8-12 weeks)
- Final Assessment/Discontinuation of documentation
- 1-year follow-up for patients who discontinue therapy: Survival form (every 6 months thereafter)

Safety Criteria

In contrast to the usual procedure in clinical trials, patients will not be selected at the start of treatment (baseline) for this register. According to Amendment VI, this investigation may provide new information on the safety of sunitinib, temsirolimus, and axitinib following sunitinib and other therapeutic options.

It is intended to document any intolerances that the physician observes during the observation period related to the documented medicinal products. Additionally, adverse events (AEs) and serious adverse events (SAEs) will be collected, as defined below.

In addition, the physician's subjective assessment of tolerability of the therapy will be obtained at each visit.

Efficacy Criteria

The efficacy of treatment with temsirolimus, sunitinib and axitinib will be assessed during routine treatment evaluation and documented at each visit based on the following tools (examinations):

[figure not shown]
- Computed tomography (if available) and/or
- Magnetic resonance imaging (MRI) (if available)
- Ultrasound examination (if available)
- Chest X-ray (if available)

The following criteria will be used to assess efficacy:

- Survival time (OS)
- Progression-free time (PFS)
- Physician's assessment of therapy response (CR, PR, SD, PD)
- Physician's assessment of efficacy and tolerability of the therapy

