The following is a schematic of all parameters to be recorded as part of this registry (imaging examination results if available).

Flow chart for the registry course for GIST and MCL

	Enrollment visit	Follow-up visit (every 8-12 weeks)	Completion Exam/ Discontinuation	Survival sheet (12 months after completion/ discontinuation)
Demographic data	X	X	X	Х
Inclusion/exclusion criteria	X			
Patient Informed Consent	X			
Tumor history	X			
Karnofsky Performance	X	X		
Treatment/Medication				
Pretreatment	X			
Concomitant medication	X			
Tumortherapy	X	X		Х
Safety				
Concomitant diseases/physical	X			
Lab values	X	X		
Electrocardiogram	X	X		
Documentation of adverse events		X	X	
Efficacy				
Subjective prognostic assessment by	X			
CT/MRI scan	X	X		
Ultra sound	X	X		
Chest X-ray	X	X		
Assessment of response to therapy by		X		
Therapy assessment of efficacy and tolerability		X		
Physician's overall assessment of therapy response			X	

Flow chart of mRCC sequence documentation:

	1 0 1		Interim documentation for non-Pfizer products	2. P	fizer Therapy Seq	SurvivalSheets		
	Enrollment Visit	Follow-up visit every 8-12 weeks	Completion/ Discontinuation of Documentation	Interim documentation every 8-12 weeks	Initial visit to change treatment	Follow-up visit every 8-12 weeks	Completion/ Discontinuation of Documentation	Survival Sheet 12 months after discontinuation, then every 6 months
Demographic data	X	X	X		X	X	X	X
Inclusion/exclusion criteria	X							
Patient Informed Consent	X			(x)				
Tumorhistory	X				X			
Karnofsky Performance Status/Height/Weight	X	X			X	X		
Treatment/ Medication								
Pretreatment	X							
Concomitant medication	X				X			
Tumor therapy	X	X		X	X	X		X
Safety								
Concomitant disease(s)/physical exam	X				X			

Labvalues	X	X			X	X		
Blood pressure	X	X			X	X		
Electrocardiogram	X	X			X	X		
Echocardiogram	X	X			X	X		
Pa in a ssessment	X	X			X	X		
Documentation of adverse events		X	X	X	X	X	X	
Efficacy		•				•		
Subjective prognosis assessment by the physician	X				X			
CT/MRI scan	X	X				X		
Ultra sound	X	X				X		
Chest X-ray	X	X				X		
Tumor Assessment		X		Х		X		
Physician's assessment of efficacy and tolera bility of the therapy		X				X		
Global assessment of therapy response by the physician			X	х			X	

Patient Quality of Life Survey	X	X			X	X		
-----------------------------------	---	---	--	--	---	---	--	--

Biometric evaluation

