7 HANDLING OF MISSING VALUES

Generally, missing values still missing after performing quality improvement measures (edit checks, queries) were performed, will not be replaced

For determining the risk groups according to Motzer score, modified Motzer score and Motzer score for pretreated patients the following procedures will be kept to:

- If at least three (two for Motzer score for pretreated patients) risk factors are present, missing values for the remaining can be ignored and the patient will be assigned to the poor risk group.
- If the calcium value is given, but the albumin value is missing, than calcium will be interpreted as a risk factor if the calcium value is above 11 mg/dL.
- If the hemoglobin value is missing, but a clinically significant low hemoglobin value or anemia is documented as comorbidity, than this will be interpreted as a risk factor present.
- If the LDH value is missing, but a clinically significant high LDH value is documented as comorbidity, than this will be interpreted as a risk factor present.

With the protocol amendment including mRCC patients being treated with axitinib some additional information was asked for in the CRF. This implies missing values for patients documented under earlier versions of protocol and CRF. The percentage of missings due to this reason will not be reported in tables extra. With amendment VI interim treatment with non-Pfizer products was included. This data will only be analyzed for patients documented under amendment VI.

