Description Table No. Title Treatment/ **Analysis set** Indication .1 Risk groups according to MIPI score at time of 2.3-2 Kaplan-Meier estimates for Progression free MCL EAS survival by patient risk groups primary diagnosis .2 Risk groups according to current MIPI score .3 2nd and 3rd line .4 2nd to 4th line .5 4th line and beyond .6 5th line and beyond .7 Patients with OR (CR+PR) .8 Patients with MR + SD .9 Patients with clinical benefit (CR+PR+MR+SD) Kaplan-Meier curves incl. Log-Rank-Test .1 PFS all patients excluding "not assessable" patients .2 PFS patients with OR (CR+PR) vs. (MR+SD) .3 PFS patients with clinical benefit (CR+PR+MR+SD) .4 PFS Temsirolimus 2^{nd} to 4^{th} line (1-3) prior therapies) vs. 5^{th} line and beyond (≥ 4 prior therapies) .5 PFS 2^{nd} to 3^{rd} line Temsirolimus (1 – 2 prior therapies) vs. 4th line and beyond (≥ 3 prior therapies) .1 Risk groups according to Fletchers risk table Kaplan-Meier estimates for Progression free EAS 2.3-2 **GIST** survival by patient risk groups .2 Risk groups according to physician's prognosis Physician's global assessment 2.4 Frequency table by time windows and for the last 2.4 Physician's global assessment of effectiveness mRCC **EAS** documented visit: total and by physician's prognosis of patients risk and by risk groups according to Motzer score, modified Motzer score and Motzer score for pretreated patients. Frequency table by time windows and for the last 2.4 Physician's global assessment of effectiveness MCL EAS documented visit: total and by risk groups according to MIPI score at time of primary diagnosis and

PFIZER CONFIDENTIAL

according to current MIPI score.

Table No.	Title	Treatment/ Indication	Analysis set	Description
2.4	Physician's global assessment of effectiveness	GIST	EAS	Frequency table by time windows and for the last documented visit: total and by physician's prognosis of patients risk and by risk groups according to Fletchers risk table.
2.5	Course of Karnofsky performance status scale			
2.5	Course of Karnofsky performance status scale	mRCC, GIST	EAS Sequence analysis for mRCC	Sample statistics by time windows and for the last documented visit, including absolute and relative differences to baseline (in total and by patient risk groups)
2.5	Course of ECOG performance status and B-symptoms			

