2.5-1	Course of ECOG performance status	MCL	EAS	Frequency table by time windows and for the last documented visit, shift table for differences to baseline (in total and by patient risk groups)
2.5-2	Course of B-symptoms	MCL	EAS	Frequency table by time windows and for the last documented visit
2.6	FKSI-15: Course			
2.6-1	Course of FKSI-15 score	mRCC	EAS Sequence analysis	Sample statistics by time windows and for the last documented visit and absolute and relative change to baseline.
2.6-2	Course of FKSI-DRS score	mRCC	EAS Sequence analysis	Sample statistics by time windows and for the last documented visit and absolute and relative change to baseline.
2.6-3	Course of FKSI domains	mRCC	EAS Sequence analysis	Sample statistics by time windows and for the last documented visit and absolute and relative change to baseline.
2.7	EQ-5D: Course			
2.7-1	Course of EQ-5D: domains	mRCC	EAS Sequence analysis	Frequency tables by time window and for the last documented visit and shift tables to baseline
2.7-2	Course of EQ-5D-VAS	mRCC	EAS Sequence analysis	Sample statistics by time windows and for the last documented visit and absolute and relative change to baseline.

Table No.	Title	Treatment/ Indication	Analysis set	Description
2.7-3	Course of EQ-5D: TTO	mRCC	EAS Sequence analysis	Sample statistics by time windows and for the last documented visit and absolute and relative change to baseline.
3	Safety			
3.1	Display of adverse events (AE)			
3.1-1.1	Summary of adverse events	All	Safety	No. / % of patients - at risk - with AE - with drug related AE - with AE related to Pfizer treatment - with AE related to interim treatment - with SAE - with drug related SAE - with SAE related to Pfizer treatment - with SAE related to Pfizer treatment - with SAE related to interim treatment - with AE leading to permanent discontinuation of Torisel®/ Sutent® / Inlyta® - with drug related AE leading to permanent discontinuation of Torisel®/ Sutent® / Inlyta® - with SAE leading to permanent discontinuation of Torisel®/ Sutent® / Inlyta® - with drug related SAE leading to permanent discontinuation of Torisel®/ Sutent® / Inlyta® - with drug related SAE leading to permanent discontinuation of Torisel®/ Sutent® / Inlyta® - Death No. / % of AE - all AE - drug related - related to Pfizer treatment - related to interim treatment - SAE - drug related SAE - SAE related to Pfizer treatment - SAE related to interim treatment

Table No.	Title	Treatment/ Indication	Analysis set	Description

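### The FKSI-15, EQ-5D and Karnofsky course tables describe only patients still in on-drug follow-up, so later windows will look too good if stopping tracks decline

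*SAP*

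**What the plan says.** **Purpose.** Quality of life in advanced RCC is a listed objective (Protocol 6, SAP 2.2). Protocol 5.2 says that the two questionnaires "will be used to document the effect of the substances temsirolimus and/or sunitinib and/or axitinib by the patient".

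**Collection.** Protocol 11: "The patient interview in the indication area will be conducted during therapy with temsirolimus, sunitinib and axitinib at each visit". In the mRCC flow charts of both documents, quality of life and Karnofsky are marked at the baseline and follow-up visits of each Pfizer sequence. They are blank at completion/discontinuation, in the interim documentation and on the survival sheets. The GIST chart shows the same pattern for Karnofsky. Protocol 8 states that the interim form carries no patient questionnaires.

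**End of collection.** Besides death and loss or withdrawal, Protocol 11 closes the follow-up visits on: "Change in therapy or discontinuation due to intolerance to temsirolimus, sunitinib, and axitinib or progression".

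**Analysis.** FKSI-15 (Tables 2.6-1 to 2.6-3), EQ-5D VAS (2.7-2) and TTO (2.7-3) get: "Sample statistics by time windows and for the last documented visit and absolute and relative change to baseline". The EQ-5D domains (2.7-1) get frequency and shift tables on the same windows. Karnofsky (2.5) gets: "Sample statistics by time windows and for the last documented visit, including absolute and relative differences to baseline". SAP 8.2.3 sets missing data to excluded for all three instruments. SAP 7 adds that "missing values still missing after performing quality improvement measures (edit checks, queries) were performed, will not be replaced". SAP 5 repeats these tables by treatment sequence.

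**The concern.** Death, progression and intolerance end the measurements, and they are also the events that go with falling quality of life and performance status. A patient who leaves drops out of every later window, and no planned method links the scores to leaving. Change from baseline does not cure this, because the patients who remain are selected on their change.

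What is at stake is interpretation. A flat or improving late-window mean could be read as the drug preserving quality of life when it shows only who is left. The distortion also differs between drugs with different observation times, and between sequence groups. SAP 5 separates patients with and without further therapy, so their exit patterns differ by construction. Protocol 11 announces a comparison of the safety and efficacy of the three drugs, but its discussion of bias deals with selection into the registry and confounding, not with selection out of follow-up.

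**Working it through.** The plan states no effect, SD or dropout figure for these scores, so there is none to reproduce. Steps 2 to 4 are illustrations.

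**1. Who is in a later window.** A score needs a follow-up visit on a Pfizer drug. Follow-up visits stop at death, withdrawal, change of therapy, intolerance or progression. Missing scores are excluded. So a window after exit cannot contain the leaver. A patient who exits before the first follow-up has a baseline and no post-baseline value.

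**2. Share still observed.** Input from Protocol 6: "Average observation period per patient: 6 months for temsirolimus, 12 months for sunitinib, 6 months for axitinib". Assuming exponential time under observation, share = exp(−t/m), with t = 1.84, 2.76, 5.98 and 11.96 months.

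| Mean m | Week 8 | Week 12 | Week 26 | Week 52 |
|---|---|---|---|---|
| 6 months | 0.736 | 0.631 | 0.369 | 0.136 |
| 12 months | 0.858 | 0.795 | 0.608 | 0.369 |

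With a first follow-up at week 8 to 12, 26–37% (6-month drugs) and 14–21% (sunitinib) would have no post-baseline value.

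**3. Effect on mean change, in baseline SDs.** Assumptions: change at month t is b·t, with b normal, mean −0.08 and SD 0.05 or 0.10 per month. The hazard of leaving is h0·exp(−k·b·t), with k = ln(HR) and HR = 1.5, 2 or 3 per SD of decline; h0 is set to give the planned average observation. Then S(t|b) = exp{−h0(1 − e^(−kbt))/(kb)}. The on-drug mean change is E[b·t·S]/E[S], and understatement is 1 − on-drug/all.

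Mean change for all patients: −0.08 × 6 = −0.48 and −0.08 × 12 = −0.96. On-drug means with slope SD 0.10:

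| | All | HR 1.5 | HR 2 | HR 3 | Understated |
|---|---|---|---|---|---|
| 6-month drugs, month 6 | −0.48 | −0.40 | −0.35 | −0.27 | 17–44% |
| 6-month drugs, month 12 | −0.96 | −0.34 | 0.00 | +0.30 | 65% to over 100% |
| Sunitinib, month 6 | −0.48 | −0.45 | −0.42 | −0.39 | 7–20% |
| Sunitinib, month 12 | −0.96 | −0.64 | −0.45 | −0.20 | 34–80% |

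For example, 1 − 0.40/0.48 = 17% (some percentages come from unrounded means). With slope SD 0.05 the four rows become 4–10%, 17–46%, 2–5% and 8–22%. With HR 1 the bias is zero.

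The upper ends depend on calibration. An improving patient's hazard falls towards zero, so fixing the average needs a cut-off on time under observation. Integrating the formula with cut-offs of 24, 36 and 60 months gives 43%, 46% and 51% for the 6-month drugs at month 6 with HR 3 and SD 0.10; longer cut-offs give more. Repeat runs reached 52% there, and 23% and 89% for sunitinib at months 6 and 12.

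**4. A second model, in FKSI-15 points.** Assumptions: baseline 42 (SD 9), slope −0.5 per month (SD 0.7), measurement SD 5, visits every 10 weeks, hazard ratio per 10 points lower score of 1.0, 1.35 or 1.82. At about 11.5 months the all-patient mean change is about −5.8.

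| Hazard ratio | On-drug change, 6-month mean | On-drug change, 12-month mean | Last-visit change, 6-month mean | Last-visit change, 12-month mean |
|---|---|---|---|---|
| 1.0 | −5.8 | −5.7 | −3.6 | −5.6 |
| 1.35 | −3.8 | −4.6 | −2.9 | −4.5 |
| 1.82 | −2.3 | −3.5 | −2.5 | −3.8 |

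At about 4.6 months the on-drug change is only 0.1 to 0.4 points too good when stopping depends on the score.

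**5. The last-visit summary.** It keeps a leaver's last on-drug value, but it also drifts upwards as stopping becomes informative, and 18–36% of simulated patients had no post-baseline value to enter. Even at hazard ratio 1.0 it differs between the observation times (−3.6 against −5.6), because the last visit falls at different times. It does not support side-by-side reading of drugs.

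**The case against.** Several points on the other side stand.

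- A reader might infer that no patient who progressed or became intolerant contributes to a window. The documents do not support that. Tumour assessment, the physician's assessment of efficacy and tolerability, and the quality of life survey share the same follow-up visit. SAP Appendix A1.3 also expects progression dates within a visit. A patient found progressing or intolerant there can still supply that visit's score.
- A reader might also infer that leavers vanish from the tables altogether. The last-visit summary retains those with a follow-up value, and patients who start a second Pfizer drug are measured again at its baseline.
- Protocol 11 asks for interviews during therapy and describes the evaluation as purely descriptive; SAP 4 has no hypotheses. No controlled effect on quality of life is estimated. On-treatment quality of life is a legitimate target if it is named as such.
- Context is partly planned: patients by window (Table 1.1-6.2), reasons for discontinuation (1.1-4), and Kaplan-Meier analyses of OS, PFS and treatment duration. Shrinking denominators will be visible. What those tables do not show is why patients are missing from a given window, or how their scores ran before they left.
- The sizes rest on inputs that the documents do not give. Halving the slope SD cuts them sharply, and the largest arise where only about 14% of the 6-month group remains. Step 2 assumes constant exit from day 0, although visit timing is left to local practice.

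These points limit the claim to later windows and to interpretation. They do not remove the selection, and Protocol 5.2 does present the questionnaires as documenting the drugs' effect.

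**Conclusion.** The point holds in a limited form. As planned, each later window in Tables 2.5 (mRCC, GIST), 2.6 and 2.7 describes patients still in on-drug follow-up, and nothing in the SAP adjusts for, or displays, how the others left. If stopping tracks decline, which the named exits make likely, later windows look too good, and more so for temsirolimus and axitinib than for sunitinib.

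It would go too far to say that the tables are certain to be biased, or by a known amount. The bias is zero if stopping is unrelated to the score. Across the assumed baseline-SD models (decline 0.08 SD per month, slope SD 0.05–0.10, hazard ratio 1.5–3 per SD), understatement at 6 months is about 4–52% for the 6-month drugs and 2–23% for sunitinib. At 12 months it is about 17% to over 100%, and 8–89%. The direction and the ordering of the drugs are firmer than any of these figures.

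**What to change.** In SAP 8.2.3 and Tables 2.5 (mRCC, GIST), 2.6 and 2.7:

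1. Repeat the course tables by time and reason of leaving, with the baseline mean of each group. An example grouping is: left before week 26 for death, progression or intolerance; left for another reason; remained.
2. In each window print the number with a baseline value, measured, still on drug, stopped by reason, and dead.
3. Title the existing tables *patients remaining on treatment*. State that later windows, and side-by-side reading across drugs, lines or sequences, are not to be taken as the drug's effect on quality of life.

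All of this uses data already collected: scores, discontinuation reasons and death dates. The cost is SAP wording and a few extra tables, some with small groups. The planned schedule collects no scores at discontinuation or on the survival sheets, so that limitation should be stated in the report.

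A time-to-deterioration analysis that counts death and treatment failure as events is optional only. It needs a pre-set threshold that the documents do not give, and it overlaps with PFS and treatment duration.
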